16.5 Study Discontinuation

A. Premature termination is only possible:

- 1) If no positive decision is obtained with regard to the research or if the judgment of the FDA or competent medical research ethics committee that has assessed the research is irrevocably revoked;
- 2) If a reasonable case can be made for terminating the research in the interest of the subjects' health;
- 3) If it transpires that continuation of research cannot serve any scientific purpose, and this is confirmed by the medical research ethics committee that has issued a positive decision on the research;
- 4) If the FDA or other Competent Authority (CA) has made an irrevocable objection;
- 5) If one of the two parties (sponsor or institution) has been declared insolvent, or if a petition has been filed for liquidation of one of the two parties;
- 6) If one of the two parties fails to comply with the obligations arising from the agreement and, provided compliance is not permanently impossible, this compliance has not taken place within thirty days after the defaulting party has received written request to comply, unless failure to comply is out of reasonable proportion to the premature termination of the research.

B. When terminating the study, the sponsor and Investigator will assure that adequate consideration is given to the protection of the subjects' interests.

16.6 Study Audits

The sponsor and representatives of regulatory health authorities are permitted to inspect the study documents (protocol, case report forms, study-related medical records, study correspondence with EC and sponsor, etc.). In addition to ongoing monitoring of the study, GCP audits by the sponsor or its representatives are also permitted. All attempts will be made to preserve subject confidentiality.

17 Deviations

17.1 Definitions

- A. A study deviation is defined as any event or change where the Investigator or site personnel did not conduct the study in compliance with the protocol as agreed to by a signed contract.
- B. Major Deviation / Violation:
Any deviation that may affect subject's rights, safety and well-being, or the scientific integrity of the clinical investigation, for example:
 - 1) any deviation from subject inclusion and exclusion criteria;
 - 2) any deviation from subject informed consent procedures (e.g., failure to obtain informed consent or failure to obtain informed consent prior to study entry);
 - 3) failure to report a serious adverse event or unanticipated adverse device effect within applicable regulatory timeframes;
 - 4) device accountability issues (e.g., missing or lost investigational product); or
 - 5) device misuse / unauthorized device use.
- C. Minor deviation:
a deviation that does not affect subject's rights, safety and well-being, or as a singular event, will not impact the scientific integrity of the clinical investigation. Examples of deviations of this type include a follow up visit conducted outside the visit window or failure of the research subject to accurately complete a study-required questionnaire not associated with a primary endpoint.

17.2 Policy

The Investigator is not allowed to deviate from the protocol without prior written agreement by the sponsor and, except as noted below, prior review and documented approval/favorable opinion from the IRB/EC.

- A. Under emergency circumstances, deviation from the protocol to protect the rights, safety and well-being of a study subject may proceed without prior approval of the sponsor and the IRB/EC. Such deviations shall be documented and reported to the sponsor and to the IRB/EC as soon as possible.
- B. Minor deviations as defined above may be initiated based on sponsor approval alone, without notification to or approval of the IRB/EC.

17.3 Procedure

In the event of an occurrence of unapproved deviation:

- A. The Investigator, or person designated by the Investigator should document and explain any deviation from the approved protocol on the designated deviation case report form as soon as they become aware of the deviation.
 - 1) Deviations must be reported to the sponsor regardless of the extent to which a deviation was medically justifiable.
 - 2) Deviations must be reported to the sponsor regardless of whether a specific subject is involved, e.g. unauthorized use of a study device outside the study, unauthorized use of a study device by a physician who has not signed an Investigator Agreement, etc.
 - 3) The explanation should include the dates of and reason for each deviation, and include discussion of any corrective action made by the Principal Investigator(s) or designated site staff to prevent recurrence of the deviation.
- B. The sponsor shall continuously monitor occurrences of protocol deviations and review Investigator-initiated corrective actions for adequacy. The sponsor will classify each deviation as major or minor per the definitions above and will:
 - 1) review the investigator's assessment of all deviations and determine and document in writing whether the deviation may affect subject's rights, safety and well-being, or the scientific integrity of the clinical investigation; these assessments will be reviewed by the independent Medical Advisory Board,
 - 2) report or ensure reporting by the PI to the IRB / EC of all protocol violations adverse events and device deficiencies that could have led to a serious adverse device effect as soon as possible, but in no event later than 10 working days after the investigator first learns of the occurrence,

- C. The sponsor may initiate an audit of the clinical investigation at a clinical site as a result of serious or repeated protocol deviations.
- D. The sponsor will consider terminating or suspending the participation of a particular investigation site or investigator if monitoring or auditing identifies serious or repeated deviations on the part of the investigator.
- E. A list of site-specific study deviations will be included in the Annual Progress Report and as part of the Final Report upon completion of the study.

18 Device Accountability

Access to the investigational devices shall be controlled and the investigational devices shall be used only in the clinical investigation with Sponsor approval and according to the protocol. The Investigator or an authorized designee shall maintain adequate records documenting the receipt, use, return, and disposal of all investigational devices, which shall include,

- A. The date of receipt
- B. Identification of each investigational device (batch number, lot/serial number or unique code),
- C. The expiry date, if applicable,
- D. The date(s) of use,
- E. Identification of the subject on whom the device was used,
- F. The date of return of unused, expired or malfunctioning investigational devices.

When the enrollment is complete, the Investigator shall return to the study sponsor any unused devices and a copy of the completed device inventory.

19 **STATISTICAL CONSIDERATIONS**

19.1 Sample Size

A. Reduction in Menstrual Blood Loss (MBL) at 12 months

Ho: Population proportion of MBL success < 0.45

Ha: Population proportion of MBL success ≥ 0.45

In order to claim study success for MBL, the lower limit of the 95% confidence interval must be ≥ 0.45 .

Under the assumption that the MBL success rate is at least 0.60, a sample size of 125 subjects provides better than 90% power to demonstrate that the lower limit of the 95% confidence interval exceeds the pre-specified threshold.

B. Rate of surgical re-intervention for HMB

Ho: Population proportion of no surgical re-intervention success < 0.75

Ha: Population proportion of no surgical re-intervention success ≥ 0.75

In order to claim study success for surgical re-intervention, the lower limit of the 95% confidence interval must be ≥ 0.75 . Under the assumption that the no surgical re-intervention success rate is at least 0.9, a sample size of 75 provides better than 90% power to demonstrate that the lower limit of the 95% confidence interval exceeds the pre-specified threshold.

C. Allowance for expected dropout rate

To account for an assumed 15% subject dropout rate (subjects lost to follow-up at the 12-month visit), a sample size of 147 treated subjects will be enrolled and treated.

19.2 Investigative Centers

The clinical study will be conducted under a common protocol for each investigational site with the intention of pooling the data for analysis. Every effort will be made to promote consistency in study execution at each investigational site. At least half of the investigational sites and 50% of the subjects will be from the United States. The study is intended to be conducted in a manner such that a target of at least 7 subjects will be enrolled for any study site. Sites enrolling fewer than 7 subjects will be pooled for analysis.

The consistency of treatment response will be investigated across the analysis centers subsequent to combining the data as described above. To verify that the success rate is similar among the analysis centers, an analysis will be performed to compare the results for each of the co-primary efficacy endpoints among analysis centers using a two-tailed test with α of 0.15. If the result is not statistically significant, the sites will be pooled for the analysis. If the result is statistically significant, a weighted average will be used for the analysis.

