5.6.4.1 Primary Efficacy Analysis

Table 3 describes the two co-primary endpoints. Each subject will be determined to be a Success or Failure per the subject success criteria. For the endpoint of Reduction in Menstrual Blood Loss, the count and percentage of subjects with Success and Failure will be summarized, along with the 95% exact confidence interval for the percent successes. The rate of surgical reintervention during 12 months, along with 95% confidence interval, will be determined using Life-Table methods. Each endpoint has a pre-specified study success criterion, as described in Table 3. Study success is achieved if both of study success criteria are met.

Table 3: Co-Primary Endpoints and Success Criteria

Co-Primary Endpoint	Test Method	Subject Success Criteria ^a	Study Success Criteria
Reduction in MBL at 12 months	Modified pictorial blood loss assessment chart (PBAC)	≥ 50% reduction in PBAC score, and a final PBAC score < 250	LCL of the percentage of subject success ≥ 45%
Rate of surgical reintervention for HMB due to treatment failure at 12 months	Surgical reintervention for HMB due to treatment failure	No surgical reintervention for HMB due to treatment failure at 12 months	LCL of the percentage of subject success ≥ 75%

^a Subject success is calculated separately for the two co-primary endpoints, such that it is possible for a subject to be considered a success for one co-primary endpoint and not for the other.

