5.6.8.4 Multicenter Studies

The clinical study will be conducted under a common protocol for each investigational site with the intention of pooling the data for analysis. Every effort will be made to promote consistency in study execution at each investigational site. At least half of the investigational sites and 50% of the subjects will be from the United States. The study is intended to be conducted in a manner such that a minimum of 7 subjects will be enrolled for any investigator. Investigational sites enrolling fewer than 7 subjects will be combined, within country, using the following process. The investigator with the smallest enrollment will be combined with the investigator with the largest enrollment. If there is a further need to combine data (still fewer than 7 subjects), then the data of the investigator with the second smallest enrollment will be combined, and so on. Once 7 subjects have been achieved, the process will continue to until all investigators with less than 7

subjects have been included in a group containing 7 or more subjects. The process of combining investigator data that have insufficient subjects will result in redefining the groups of investigators for the purposes of investigating pooling. These combined groups will be referred to as "analysis centers".

The consistency of treatment response will be investigated across the analysis centers subsequent to combining the data as described above. To verify that the success rate is similar among the analysis centers, an analysis will be performed to compare the results for each of the co-primary efficacy endpoints among analysis centers using a two-tailed test with α of 0.15. The MBL endpoint will be analyzed using a logistic regression. The surgical reintervention endpoint will be analyzed using Life-Table methods.

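### Protocol 19.2 switches a co-primary analysis to an unspecified weighted average after a significant centre test, while the SAP gives that test no consequence

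*Protocol*

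**What the plan says.** Protocol 19.2 compares each co-primary endpoint across analysis centres "using a two-tailed test with α of 0.15". It then sets out two branches. "If the result is not statistically significant, the sites will be pooled for the analysis". Otherwise: "If the result is statistically significant, a weighted average will be used for the analysis". It names no weights, variance or interval method. Protocol 19.4 refers the reader to the SAP for further detail.

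SAP 5.6.8.4 repeats the test at the same level and adds the methods: "The MBL endpoint will be analyzed using a logistic regression", and "The surgical reintervention endpoint will be analyzed using Life-Table methods". It says nothing about what follows from a significant result, and the SAP never mentions a weighted average.

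SAP 5.6.4.1 gives one primary analysis per endpoint, with no condition on the centre test. MBL success is summarised "along with the 95% exact confidence interval for the percent successes". For the other endpoint: "The rate of surgical reintervention during 12 months, along with 95% confidence interval, will be determined using Life-Table methods". The success thresholds are lower limits of at least 45% and 75%. SAP 5.6.8.1 plans no covariate adjustment. The SAP's table index lists a pooling analysis and a by-centre summary (Tables 14.2.3.1.1 and 14.2.3.1.2) but no centre-weighted primary analysis.

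**The concern.** After a significant centre test, the protocol points to one primary analysis and the SAP to another, and the protocol's version cannot be carried out as written. A weighted average of centre rates needs weights, and a lower limit for it needs a variance and an interval method. An exact binomial interval does not in general carry over to a weighted average.

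The choice would therefore be made after the data, including the by-centre results, are available. If the result lies near 45% or 75%, that choice could decide whether the study succeeds. The trigger is a liberal test applied to many small centres, so it will often fire by chance.

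**Working it through.** **Inputs.** From Protocol 19.1 and SAP 5.6.7: MBL threshold 0.45, assumed rate 0.60, n = 125; reintervention-free threshold 0.75, assumed rate 0.90, n = 75; 147 treated after 15% dropout (protocol). From Protocol 19.2: centre test at 0.15, target of at least 7 women per site. The documents do not give the number or size of analysis centres or the exact form of the test, so these are assumed below. Reintervention is treated as binary, without censoring.

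**1. The plan's own figure.** Find the smallest success count r whose exact two-sided 95% lower limit reaches the threshold, then take binomial tail probabilities.

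| n | Threshold / assumed rate | r | Lower limit at r | One-sided type I error | Power |
|---|---|---|---|---|---|
| 125 | 0.45 / 0.60 | 68 | 0.4525 | 0.0218 | 0.914 |
| 147 | 0.45 / 0.60 | 79 | 0.4534 | 0.0206 | 0.948 |
| 75 | 0.75 / 0.90 | 64 | 0.7527 | 0.0221 | 0.931 |

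Both stated sample sizes (125 and 75) reproduce, and 125/0.85 = 147.06. The 125 corresponds to the pooled exact analysis with no switch.

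**2. How often the switch fires with no true centre differences.** Nominally 15% per endpoint; for at least one of two independent tests, 1 − 0.85² = 27.75%. Simulated Pearson tests fired in about 12–15% of trials. Likelihood-ratio tests, whose chi-square approximation is poor in small centres, fired in 19–26% for MBL and 19–24% for reintervention.

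**3. What the weights do to the estimate.** With size weights, Σnᵢpᵢ/N equals the pooled proportion exactly, so only the interval is open. Equal weights can differ a good deal: in a constructed example of 147 women, the pooled and size-weighted rates are both 86/147 = 58.5%, while the equal-weighted rate is 66.5%.

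**4. What the weights do to the error rate.** Simulation of 147 women in three assumed centre layouts: Pearson test, switch to the weighted limit (normal theory) if significant, pooled exact limit otherwise. The intended one-sided level is 2.5%.

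| Rule after a significant test | MBL, true rate 45% | Reintervention-free, true rate 75% |
|---|---|---|
| Size or equal weights | 2.2–2.4% | 2.7–2.9% |
| Inverse-variance weights, 0.5 correction | 2.8–3.2% | 7.5–8.8% |

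Without the switch, the pooled analysis gives 2.0–2.4% over the two endpoints. Inverse-variance weighting does most harm for reintervention because centres with high observed success have small estimated variances and so receive the most weight.

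**5. Inverse-variance weights without a correction.** A centre of m women with no reintervention has estimated variance zero, so its weight is undefined. At the planned 10% event rate this has probability 0.9^m: 0.478 for m = 7 and 0.349 for m = 10. The chance of at least one such centre among k is 1 − (1 − 0.9^m)^k: above 0.999 for 21 centres of 7, 0.998 for 14 of 10, 0.926 for 10 of 14, and 0.556 for 7 of 21. In simulated layouts of 10 to 21 centres, at least one was present in 99.5–100% of trials with a significant Pearson test.

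**6. How often the decision changes.** At a true MBL rate of 53%, at least one of the three weightings reversed the pooled decision in 20–28% of triggered trials. With a 15% trigger that is 0.15 × 0.20 = 3.0% to 0.15 × 0.28 = 4.2% of all trials. At the planned rates, reversals occurred in 4–8% of triggered trials for MBL (60%) and under 0.5% for reintervention (90%).

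**The case against.** The strongest reply is that this is a missing detail. The SAP does not forbid weighting; it is silent, and Protocol 19.4 says details belong there. Weighting by centre size leaves the MBL proportion unchanged, so the SAP's exact interval could still be reported for it. Stating the weights and interval in advance would also close the gap. All of that stands, and it means the discrepancy is one of omission, not of two instructions that contradict each other. It does not remove the problem: the weights are not stated anywhere, and a significant result leaves two candidate analyses.

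A reader might infer that the weighted average often cannot be computed for reintervention. The documents do not support that. It is true only of uncorrected inverse-variance weights, which the protocol does not name; size and equal weights can always be computed.

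A reader might also infer that the two documents contradict each other on forming centres. Protocol 19.2 says only that sites with fewer than 7 women will be pooled. The SAP merges them within country: "The investigator with the smallest enrollment will be combined with the investigator with the largest enrollment". That can be read as compatible detail. A cross-reference is enough.

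Finally, the trigger rates above 15% depend on a likelihood-ratio test. The SAP names logistic regression for MBL without fixing the test, and life-table methods for reintervention, which the binary simulation only approximates.

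**Conclusion.** The point holds in this form: the protocol makes the analysis that decides each co-primary endpoint depend on a centre test at 0.15, leaves the resulting analysis undefined, and is not matched by the SAP. By chance alone this arises in about 15% of trials per endpoint, and in up to about 25% with a likelihood-ratio test.

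It would be too strong to say that the switch grossly inflates error. With size or equal weights it hardly moves the error rate. The clear inflation, to about 7.5–8.8% for reintervention against an intended 2.5%, requires corrected inverse-variance weights, one choice among several that the wording allows. If the true rates are near 60% and 90%, the choice will rarely matter. The exposure is a borderline result with an unsettled rule.

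The error rates and reversal frequencies rest on assumed centre layouts, a Pearson test, normal-theory limits after the switch and no censoring. The gap in the text rests on none of these. It should be reconciled before database lock.

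**What to change.** 1. Delete the switch from Protocol 19.2. State there and in SAP 5.6.4.1 that the pooled exact interval (MBL) and the pooled life-table limit (reintervention) decide study success whatever the centre test shows.
2. Keep the centre test and the two by-centre tables already planned, as a heterogeneity report.
3. If a centre-weighted or random-centre analysis is wanted, make it a sensitivity analysis in the SAP, with weights, treatment of zero-event centres and interval method fixed in advance. For reintervention it should respect the censoring that SAP 5.6.8.2 provides for.
4. Have Protocol 19.2 refer to the within-country rule in SAP 5.6.8.4 for forming analysis centres.

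The cost is about a sentence in each document, one cross-reference and, if wanted, one sensitivity analysis. The sample size does not change: 125 already matches the pooled exact MBL analysis.

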19.3 Efficacy Analyses

A. Primary Efficacy Analysis

Each subject will be determined to be a Success or Failure per the subject success criteria. Subject success is calculated separately for the two co-primary endpoints, such that it is possible for a subject to be considered a success for one co-primary endpoint and not for the other.

B. Secondary Efficacy Analysis

Secondary endpoints will be summarized using descriptive statistics.

19.4 Other

Additional details, including handling of dropouts or missing data, are described in the study Statistical Analysis Plan referenced in Section 2.

20 ADMINISTRATIVE REQUIREMENTS

20.1 Institutional Review Board/Ethics Committee Approval

Before commencement of the study, each investigator must provide Gynesonics Inc. with written documentation of IRB/EC approval of both the protocol and the informed consent form, which must comply with all requirements outlined by Gynesonics. The approval letter must specify the documents and document revision and/or date being approved. If an Investigator is also a member of the review committee, the Investigator must not participate in the committee decision; non-participation must be noted in the approval letter.

20.2 Competent Authority

Gynesonics Inc. is responsible for obtaining regulatory approval for the study from the relevant Competent Authority as per national requirements.

21 PERSONNEL RESPONSIBILITIES

21.1 Site Principal Investigator

- 1) Ensure that the rights, safety, and welfare of subjects are protected
- 2) Implement study in accordance with protocol
- 3) Possess thorough knowledge of the appropriate use of the study device as described in the protocol, instructions for use, and other information sources provided by the sponsor
- 4) Ensure sufficient study resources and staffing to enable proper conduct of study and timely completion of case report forms
- 5) Delegate significant study-related duties only to appropriately qualified and trained staff
- 6) Permit inspection of facilities and records by the study monitor and any governing regulatory agencies
- 7) Submit protocol and informed consent and other subject materials, and substantive amendments, to the IRB/EC and await approval.
- 8) Obtain informed consent of subjects
- 9) Complete case report forms; Ensure the accuracy, completeness, legibility, logic, contemporaneousness, and attribution of data reported to the sponsor
- 10) Record and explain deviations from protocol and report to monitor
- 11) Submit annual progress reports, final reports, and adverse effect reports to the EC and sponsor
- 12) Record the receipt, disposition, and return of study devices
- 13) Maintain medical histories of subjects
- 14) Retain records for the longer of 1) three years following study completion, or 2) local ministry of health regulations concerning required study document retention
- 15) Notify the sponsor prior to disposal of any records and to allow the sponsor to make other arrangements for on-going storage of study records

